## 6.3 Eligibility criteria

### 6.3.1. Inclusion criteria

Patients meeting all of the following criteria will be considered for enrolment into the study:

INCL1.	Male and female patients aged $\geq 18$ years at the time of signing the Informed Consent Form.
INCL2.	Subjects with a diagnosis of psoriatic arthritis as per the Classification for Psoriatic Arthritis (CASPAR) criteria (see appendix 3 ) confirmed up to 24 months prior to screening.
INCL3.	Subjects with active PsA defined as the presence of at least 3/78 tender and at least 3/76 swollen joints (see section 8.2.3 and section 8.2.4 ) or 2 swollen and 2 tender joints plus one affected entheseal site (Achilles tendon and/or plantar fascia) at baseline.

INCL4.	Are capable of understanding and signing an informed consent form.
INCL5.	Women of childbearing potential or men capable of fathering children must be using adequate birth control measures (e.g.: abstinence, oral contraceptives, intrauterine device, barrier method with spermicide, surgical sterilization) during the study and for 6 months after receiving the last administration of study agent. Female subjects of childbearing potential must test negative for pregnancy. Female subjects must agree to not donate eggs (ova, oocytes) during the study and for 6 months after last dose of study agent. Male subjects must agree to not donate sperm while in the study and for 6 months after last dose of study agent.
INCL6.	Patients fulfilling the following TB criteria:
INCL6.1.	Have no history of latent or active TB prior to screening. An exception is made for subjects with a history of latent TB and documentation of having completed appropriate treatment for latent TB 3 years prior to the first administration of study agent. It is the responsibility of the investigator to verify the adequacy of previous antituberculous treatment and provide appropriate documentation.
INCL6.2.	Have no signs or symptoms suggestive of active TB upon medical history and/or physical examination.
INCL6.3.	Have had no close contact with a person with active TB or, if there has been such a contact, will be referred to a physician specializing in TB to undergo additional evaluation, and if warranted, receive appropriate treatment as if having latent TB prior to or simultaneously with the first administration of study agent.

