#### **11.5.2. Secondary endpoint analyses**

Full descriptive data will be provided for all secondary endpoints. Adjusted estimates of effect size will be obtained for binary secondary endpoints using multiple binary logistic regression; odds ratios and 95% confidence intervals will be presented. Continuous interval outcomes will be analysed using multiple linear regression; differences between treatment group means and 95% confidence intervals will be presented. Count outcomes will be analysed using an appropriate generalised linear model; incident rate ratios and 95% confidence intervals will be presented. Severely skewed outcomes for which an appropriate generalised linear model cannot be identified will be analysed using quantile regression; differences between medians and 95% confidence intervals will be presented. All analyses will control for the stratification factor and baseline values of the outcome. Where the aim is to relate clinical or imaging responses to baseline joint counts or to symptom duration, these variables will be added to the relevant models as covariates after the initial estimate of the treatment effect has been obtained; interactions between each variable and treatment will be assessed and will be considered substantive if found to be significant at the 10% level. Planned subgroup analyses will investigate

differences in treatment response according to oligo/polyarthritis status, disease duration at baseline. The total amount of steroids received by week 12, as a post-randomisation variable, will not be adjusted for in the analysis but will instead be compared between groups.

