4.2 Selection of Study Population

Key inclusion criteria (pertinent to primary endpoint)

- Subjects with a diagnosis of psoriatic arthritis as per the Classification for Psoriatic Arthritis (CASPAR) criteria confirmed up to 24 months prior to screening.
- Subjects with active PsA defined as the presence of at least 3/78 tender and at least 3/76 swollen joints or 2 swollen and 2 tender joints plus one affected enthesal site (Achilles tendon and/or plantar fascia) at baseline.

Key exclusion criteria (pertinent to primary endpoint)

- Previous treatment with any conventional or biological DMARDs, where “treatment” is defined as a therapeutic dosage according to each product’s SmPC. Topical preparations for psoriasis are not considered DMARDs (examples include, but are not limited to, steroids, salicylic acid, tar).
- Any chronic inflammatory arthritis diagnosed before 16 years old.

- Patients who have received any systemic/intra-articular corticosteroids within 4 weeks prior to screening. Topical preparations with steroids for cutaneous use, or inhalers for the treatment of asthma are not considered systemic/intra-articular corticosteroids.

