PASI score	Psoriasis area and severity index	0 to 72	Each of four body areas (head & neck, upper limbs, trunk, lower limbs) is scored 0-4 (absent-very severe) for severity of erythema, induration and desquamation. The three scores are summed for each region, then multiplied by the surface area of each region (0.1, 0.2, 0.3 & 0.4 respectively). Each region is also scored for area of psoriasis from 0 (nil) to 6 (90-100%). The severity score is multiplied by the area score and these subtotals are added across the four regions.
mNAPSI score	Modified Nail Psoriasis Severity Index	0 to 140	Each fingernail is scored for the presence and the severity of pitting, onycholysis and nail plate crumbling (score 0-3) and the presence or absence of splinter haemorrhages, leukonychia, red

Variable Name	Description	Valid Values (Ranges)	Computation Methods, Notes or Equations
			spots in the lunula, oil spot dischromia and nail bed hyperkeratosis (score 1 for each if present). This gives a total possible score of 140.
CPDAI score	Composite psoriatic disease activity index	0 to 15	See Table 2 (below) for calculation of CPDAI including the spine
DLQI	Dermatology life quality index	0 to 30	Total of 10 questions across 6 domains scored 0 to 3
HAQ	Health assessment questionnaire disability index	0 to 3	Mean of 8 domains each scored 0-3; within each domain the maximum score is taken. If this is <2 and the patient has reports requiring help or devices for that domain, score for that domain is increased to 2.
ASQoL	Ankylosing spondylitis quality of life scale	0 to 18	Total of 18 responses (0 "No" or 1 "Yes")
SF36-PCS	Short form 36 physical component score	0 to 100	Scoring of SF36 is complex; see section 15 for syntax which corresponds to command: sf36, natver(US) stub(SF)
SF36-MCS	Short form 36 physical component score	0 to 100	Scoring of SF36 is complex; see section 15 for syntax which corresponds to command: sf36, natver(US) stub(SF)
MDA	Minimal disease activity	0 (No) to 1 (Yes)	At least 5 of the 7 following criteria: Tender joint count (/68) \leq 1 Swollen joint count (/66) \leq 1 PASI \leq 1 or BSA \leq 3 Patient pain VAS \leq 15 Patient global disease activity VAS \leq 20 HAQ \leq 0.5 Enthesitis count \leq 1.

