PsARCResponse	Psoriatic arthritis response criteria	0 (No) to 1 (Yes)	Overall response is defined by improvement from baseline assessment in 2 of 4 criteria, 1 of which must be a joint count; there must not be worsening in any of the 4 criteria: 1. At least 30% reduction in tender joint grade (total of 68 joints graded 0-3) 2. At least 30% reduction in swollen joint grade (total of 66 joints graded 0-3) 3. At least a 1 point reduction in physician's assessment of articular disease (1-5 Likert scale) 4. At least a 1 point reduction in patient's assessment of articular disease (1-5 Likert scale)
PsARCResponseSens	Psoriatic arthritis response criteria	0 (No) to 1 (Yes)	Overall response is defined by improvement from baseline assessment in 2 of 4 criteria, 1 of which must be a joint count; there must not be worsening in any of the 4 criteria: 1. At least 30% reduction in tender joint grade (total of 78 joints graded 0-3) 2. At least 30% reduction in swollen joint grade (total of 76 joints graded 0-3)

Variable Name	Description	Valid Values (Ranges)	Computation Methods, Notes or Equations
			3. At least a 1 point reduction in physician's assessment of articular disease (1-5 Likert scale) 4. At least a 1 point reduction in patient's assessment of articular disease (1-5 Likert scale)
ACR20/50/70	American college of rheumatology responder index 20 / 50 / 70	0 (No) to 1 (Yes)	The patient must have: ≥20/50/70% improvement in both TJC (68 joints count: as in appendix 8, minus CMC and DIP of the feet) and SJC (66 joints count: as in appendix 8, minus CMC and DIP of the feet) and ≥20/50/70% improvement in at least 3 of the following 5 ACR Core set criteria: 1. Patient's Assessment of Pain Visual Analogue Scale (VAS) 2. Patient's Global Assessment of Disease Activity VAS 3. Physician's Global Assessment of Disease Activity VAS 4. Patient's Assessment of Physical Function as measured by the HAQ-DI 5. Acute phase reactant as measured by CRP
PASI75	PASI 75% response	0 (No) to 1 (Yes)	Patients achieving PASI 75 are defined as having an improvement of at least 75% in the PASI compared to baseline.
US_TotalGS	US total grey scale scores across all common joints	0 to 72	Total of GS scores (0-3) for 24 joints: bilateral wrists, MCPs 2&3, PIPs 2&3, knees, MTPs 1-5, ankle

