11.2 Secondary Efficacy Variable Analysis

Full descriptive data will be provided for all secondary endpoints. Adjusted estimates of effect size will be provided for binary secondary endpoints using multiple binary logistic regression; odds ratios and 95% confidence intervals will be presented. This applies to MDA, PsARC response, ACR 20/50/70, PASI75, US remission, steroid therapy required up to week 12 (Y/N). Continuous interval outcomes will be analysed using multiple linear regression; differences between treatment group means and 95% confidence intervals will be presented. This applies to PASDAS, CPDAI, patient global VAS, SF36 PCS and MCS, US outcomes. Count outcomes will be analysed using an appropriate generalised linear model (see Table 11.2.1); incident rate ratios and 95% confidence intervals will be

presented. If negative binomial regression is used, the mean dispersion parameter will be applied. In the case of missing scores for individual joints, the exposure will be amended to indicate the number of joints/enthuses assessed. This applies to the Leeds enthesitis index, the Leeds dactylitis index, & mNAPSI. Severely skewed outcomes for which an appropriate generalised linear model cannot be identified will be analysed using quantile (median) regression; differences between medians and 95% confidence intervals will be presented. If the median is 0 in both groups then alternative point of comparison will be attempted in the following sequence until model convergence is achieved: 75th percentile, 90th percentile, 95th percentile. This applies to PASI & DLQI. All analyses will control for the stratification factor and baseline values of the outcome where relevant. Two-sided significance at $p<0.05$ will be the criterion applied to all secondary outcomes. If a statistically significant difference is not found for the primary outcome, all secondary outcomes will be considered exploratory.

Table 11.2.1: Models to be used for analysis of secondary outcomes

The appropriateness of these models has been determined following initial blind review of the data. In the event that, once allocation is known, the specified model fails to converge, an alternative model will be used and this deviation from the SAP will be highlighted in the trial report

Outcome(s)	Model
LEI	Negative binomial
LDI	Negative binomial
PASI	Quantile (median) regression
mNAPSI	Negative binomial
DLQI	Quantile (median) regression

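### The logistic models for the binary secondary endpoints have no usable baseline covariate, so they adjust in effect only for the oligo/polyarticular stratum and can lose power

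*SAP*

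**What the plan says.** SAP 11.2 assigns multiple logistic regression to MDA, PsARC response, ACR20/50/70, PASI75, US remission and the need for steroid up to week 12. The covariate rule is "All analyses will control for the stratification factor and baseline values of the outcome where relevant". SAP 11.4 repeats it for the three PASDAS status and response endpoints added after unblinding. The mixed models that SAP 11.2 holds in reserve take the same covariates.

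Protocol 11.5.2 gives the rule without the closing qualifier: "All analyses will control for the stratification factor and baseline values of the outcome". SAP 8.6 has the same unqualified sentence.

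The definitions are in SAP 8.7. For PsARC, "Overall response is defined by improvement from baseline assessment in 2 of 4 criteria". For PASI75, "Patients achieving PASI 75 are defined as having an improvement of at least 75% in the PASI compared to baseline". ACR20/50/70 are likewise percentage improvements. MDA is a state: five of seven criteria, two of which are a tender count (of 68) and a swollen count (of 66) of at most 1. Protocol 6.3.1 requires at entry the "presence of at least 3/78 tender and at least 3/76 swollen joints", or two of each plus an affected entheseal site.

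**The concern.** A baseline value of the outcome is a natural covariate for a continuous score. For a responder endpoint it is either undefined or nearly the same for everyone. Neither document names a substitute for the treatment-effect models, so baseline severity enters them only through a two-level joint-count stratum. Continuous endpoints, including the primary, carry the baseline score itself.

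What is at stake is power on the secondary endpoints and clarity about which model will be run. If baseline activity predicts the endpoint, a model that leaves it out gives up power that the trial's existing data could supply. An analyst also cannot tell from the text whether to omit the term or use a component score instead.

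**Working it through.** **Step 1. Is there a baseline value?** Endpoints and visits are from SAP 3.2.2, definitions from SAP 8.7.

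| Endpoint | Planned comparisons | Baseline response status |
|---|---|---|
| PsARC | 5 | none (improvement) |
| ACR20/50/70 | 3 × 4 = 12 | none (improvement) |
| PASI75 | 4 | none (improvement) |
| Steroid need to week 12 | 1 | none (post-randomisation event) |
| MDA | 4 | exists, nearly constant (step 2) |
| US remission | 3 | exists at screening, rate not given |

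The total is 5 + 12 + 4 + 1 + 4 + 3 = 29, of which 5 + 12 + 4 = 21 are improvement-based. SAP 11.4 adds 3 endpoints × 4 visits = 12 exploratory comparisons.

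**Step 2. MDA at baseline.** Entry needs at least two tender and two swollen joints, while MDA allows at most one of each. Both joint criteria therefore fail unless qualifying joints lie among the 78 − 68 = 10 (tender) or 76 − 66 = 10 (swollen) extra joints, which are the CMC and foot DIP joints. If both fail, a patient is in MDA only by meeting all 7 − 2 = 5 remaining criteria.

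**Step 3. What the covariate does in the model.** An all-zero column adds nothing: a design with intercept, stratum, that column and treatment has rank 3 of 4. With k baseline-positive patients and outcome probability q, the chance that all share one outcome is q^k + (1 − q)^k. For k = 2 this is 0.50 at q = 0.5 and 0.82 at q = 0.9. In those cases the coefficient cannot be estimated. Either way the model reduces to treatment plus stratum.

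**Step 4. The plan's own figure.** No power is stated for any binary endpoint. The primary calculation gives n per arm = 2 × (1.960 + 0.842)² × 1.57² / 1² = 38.7, rounded up to 39, so 78 in total. Then 39 / 0.95 = 41.1, rounded up to 42 per arm, so 84. Both figures reproduce, and 42 per arm is used below.

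**Step 5. Power with and without one continuous baseline score.** Simulation: 6,000 trials per row, 42 per arm, likelihood-ratio test, two-sided 5%. Response rates and prognostic odds ratios (OR) are assumptions, as are 50% polyarticular, a stratum log OR of −0.4 and a score independent of the stratum.

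| Rates | OR per SD of score | Stratum only | Plus score | Change (points) |
|---|---|---|---|---|
| 30% vs 60% | 1.0 | 81.4% | 80.8% | −0.6 |
| | 0.74 | 80.7% | 81.0% | +0.3 |
| | 0.55 | 81.1% | 83.1% | +2.0 |
| | 0.41 | 81.3% | 86.0% | +4.7 |
| | 0.30 | 81.7% | 89.2% | +7.5 |
| 40% vs 65% | 0.74 | 66.2% | 66.9% | +0.7 |
| | 0.55 | 65.9% | 68.5% | +2.6 |
| | 0.41 | 65.5% | 71.6% | +6.1 |
| | 0.30 | 65.1% | 74.5% | +9.4 |
| 20% vs 50% | 0.55 | 85.2% | 87.2% | +2.0 |
| | 0.30 | 83.4% | 90.6% | +7.2 |

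Type I error is 4.9% to 6.0% across the two models.

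A second simulation (4,000 trials, Wald tests) sets the correlation r of the score with a latent week-24 state. At 25% vs 50%, the gain is about 1.5 points at r = 0.3, 67% to 73% at 0.5, and 69% to 81% at 0.7. At 30% vs 60% and r = 0.5 it is 80% to 85%. Type I error is 4.3% to 4.8%. A repeat of the r = 0.7 setting gave 67% to 81%, a gain of 14, so the top of the range is uncertain by a few points.

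The two runs agree. With OR per SD ≈ exp(−1.7r / √(1 − r²)), r = 0.3, 0.5 and 0.7 correspond to about 0.59, 0.38 and 0.19.

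**Step 6. Where the gain comes from.** At 30% vs 60% and OR 0.30 per SD, the median log OR for treatment moves from 1.29 (SE 0.47) to 1.71 (SE 0.57). The ratio rises from 1.29/0.47 = 2.74 to 1.71/0.57 = 3.00. The interval on the odds-ratio scale does not narrow; the estimand becomes conditional on baseline activity.

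**The case against.** The strongest reply is that the qualifier in SAP 11.2 lets the analyst drop a covariate that does not exist, and that the resulting test keeps its error rate. Both points stand. A reader might infer that the SAP forces adjustment for a non-existent variable, or that the responder analyses are invalid; the documents support neither. But the qualifier does not say which endpoints lose the term or whether a component may replace it, and SAP 8.6 and protocol 11.5.2 lack it.

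It can also be said that SAP 8.2 interprets baseline values of response variables as their components. That gloss is confined to the imputation models. It would point to baseline PASI for PASI75, but does not choose among four PsARC components or seven ACR components.

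A reader might infer that baseline activity is ignored. It is not. The stratum is a dichotomised baseline joint count in every model, components enter the imputation, and SAP 8.6 adds joint counts or symptom duration after the initial treatment estimate.

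The power figures are open to a fair challenge. The second simulation models a week-24 state, whereas 21 of the 29 comparisons are improvement-based. On a log scale, with baseline/week-24 correlation r and SD ratio k (week 24 to baseline), the correlation of baseline with change is (rk − 1) / √(k² + 1 − 2rk). For r = 0.3, k = 1 it is −0.59; for r = 0.7, k = 2.5 it is +0.39. The assumed range includes zero, so the gain there may be nil. Steroid need is triggered by PsARC non-response (protocol 5.1) and shares this doubt. PASI75 is restricted to patients with at least 3% BSA affected, so it has fewer than 42 per arm unless everyone qualifies.

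For US remission, SAP 11.4 reports very low proportions achieving it but gives no screening rate, so near-constancy at screening is plausible, not shown. At an assumed 2% vs 8%, 42 × 0.02 + 42 × 0.08 = 4.2 events are expected, too few to support another term.

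**Conclusion.** The concern holds for the binary secondary endpoints. The stated covariate is undefined for PsARC, ACR20/50/70, PASI75 and steroid need, and almost constant for MDA, so the treatment-effect models adjust in effect only for the stratum. The rule also differs between sections and cannot be followed literally where it is unqualified.

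The consequence is a possible loss of power, not bias or an inflated error rate. One continuous baseline score is worth about 0 to 3 points if it is a weak or moderate predictor and about 4 to 12 if strong. The documents do not give prognostic strength or response rates, so the size is conditional on those assumptions; correlation between the score and the stratum would shrink it. The argument is clearest for MDA and PASDAS very low disease activity.

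It would be tempting to attribute any disagreement between the PASDAS result and the responder results to adjustment alone. The documents do not support that: the binary endpoints are also dichotomised, and SAP 8.2 imputes non-response after early withdrawal for them but carries forward withdrawal-visit data for continuous outcomes.

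The stakes are limited. These endpoints have no stated power target and become exploratory if the primary is not significant; those in SAP 11.4 are exploratory in any case. The primary ANCOVA already adjusts for baseline PASDAS.

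**What to change.** Reconcile SAP 8.6, 11.2 and 11.4 and protocol 11.5.2 by stating that baseline response status is not used in the logistic models or their mixed-model fallback. Name one continuous baseline covariate in addition to the stratum:

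- baseline PASDAS for MDA, PsARC, ACR20/50/70, steroid need and the three PASDAS endpoints in SAP 11.4;
- baseline PASI for PASI75;
- the stratum alone for US remission if events are too few.

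SAP version 4.0 is dated 15/11/2023 and includes changes marked as made after unblinding. The adjusted models should therefore be reported beside the planned ones as a labelled post-hoc sensitivity analysis, not in place of them. State that their odds ratios are conditional on baseline activity and are not directly comparable in size with the stratum-only odds ratios.

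The cost is a few sentences and one extra term per model. Protocol 8.6 already schedules the PASDAS components and PASI at baseline, so no new data are needed.

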11.3 Other Efficacy Variable Analyses

A number of sensitivity analyses will be conducted. In addition to sensitivity analyses relating to missing data or outliers (see section 8.2) and stratification status (see section 11.1), a per protocol analysis will be performed, repeating the primary endpoint analysis in the Per Protocol Set. In addition, comparisons will be made between PsARC response status calculated using the 68/66 tender/swollen counts originally specified by the criteria and response status calculated using the extended 78/76 joint counts. McNemar's tests will be used to compare response status according to the reduced and expanded joint counts. This will be performed in the observed data (i.e. without imputation).

See section 8.6 for details of planned exploratory analysis of baseline predictors of response to treatment.

In a subset of patients, total synovitis and enthesitis scores calculated in expanded sets of joints defined in the newly published OMERACT definitions will be compared between groups according to the same methods as for secondary outcomes. This will be conducted in the subset of participants with for whom the expanded joint scores were collected at screening. In addition, for patients in the WB-MRI subset the WB-MRI lesion scores will be compared between groups on an exploratory basis using the same methods as for secondary outcomes. However, the focus will be on quantifying the potential treatment effect. A range of confidence intervals (75%, 85%, 95%) around the difference between the treatment arms will be calculated, to indicate the level of confidence with which we could say there was potential for a substantive difference between groups. The biomarker sub-study data (available in a subset of patients) are to be analysed separately as part of a number of collaborative projects with other centres. Analysis plans for these projects will be produced separately.

An assessment of the test-retest reliability of the PASDAS will be performed, by calculating the intraclass correlation coefficient ($ICC_{(1,1)}$) between PASDAS measurements collected at screening and baseline; a 95% confidence interval will be constructed.

If sufficient patients in each group receive additional steroid injections at week 8, g-methods will be used to investigate the extent to which this is associated with total PDUS (US GLOESS) score at week 12.

Pearsons product-moment correlation or Spearman's rank correlation, according to data type, will be used to quantify the extent of association between tender joint count, swollen joint count and total PDUS (US GLOESS) at screening. In specific joints for which both clinical examination and ultrasound scan were performed, sensitivity and specificity of tenderness, swelling and both tenderness and swelling for detecting joints scoring more than GS<2 and PD=0 will be calculated, together with associated 95% confidence intervals via the Wilson method.

To assess the extent of association between clinical and US imaging responses to therapy, an extended Cochran-Mantel-Haenszel test, stratified on poly/oligoarthritis and randomised treatment, will be performed on 24 week MDA versus 24 week US remission.

